#### 6.3.5. Clinical Virology

6.3.5.1. Virology Testing

6.3.5.1.1. Virology Samples to Address the Study Objectives

Mid-turbinate nasal swab samples will be used to assess SARS-CoV-2 viral load by reverse transcriptase-quantitative polymerase chain reaction (RT-qPCR). Once viral load testing is complete, the remnant samples may be used to evaluate respiratory viral coinfection, SARS-CoV-2 infectious viral titer, CCI

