SARS-CoV-2 viral load results that are below LLOQ but have a positive signal will be reported as "<2228cp/mL SARSCoV2 detected" and those that are below lower limit of detection (LOD) and negative will be reported as "No SARS-CoV2 detected". The data will be imputed as follows:

- A value of 1114 copies/mL (half of the LOQ 2228 copies/mL) will be used to calculate descriptive statistics if the datum is reported as "<2228cp/mL SARSCoV2 detected".
- A value of 746.5 copies/mL (half of the LOD 1493 copies/mL) will be used to calculate descriptive statistics if the datum is reported as "No SARS-CoV2 detected".

SARS-CoV-2 infectious viral titer result will be imputed as follows:

- A value of 100 PFU/mL (half of the LOQ 200 PFU/mL) will be used to calculate descriptive statistics if the datum is reported as "< 200 PFU/mL" and the corresponding qualitative result is "Positive".
- A value of 50 PFU/mL (1/4 of the LOQ 200 PFU/mL) will be used to calculate descriptive statistics if the datum is reported as "< 200 PFU/mL" and the corresponding qualitative result is "Negative".

For baseline SARS-CoV-2 viral load, results of "No SARS-CoV2 detected", "Inconclusive", "<2228cp/mL SARSCoV2 detected" are considered as < LLOQ; numerical results are considered as \ge LLOQ.

Numerical result of SARS-CoV-2 viral load and SARS-CoV-2 infectious viral titer from samples collected with less than specified volume of test solution will not be included in viral load or infectious viral titer analyses. The positive or negative result of these samples will not be impacted.

Any SARS-CoV-2 viral load and infectious viral titer samples collected on or after the day when the participants are receiving additional COVID-19 treatments (see Appendix 3) will be excluded from the viral load or infectious viral titer analysis.

Base 10 logarithm transformation will be used for analyzing SARS-CoV-2 viral load and SARS-CoV-2 infectious viral titer.

Sparse PK concentration values that are below the limit of quantitation (BLQ) will be presented as "BLQ" in the data listing.

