6.4. Intercurrent Events

Handling of intercurrent events for the efficacy endpoints related to hospitalization, MAVs, death, symptom alleviation, SARS-CoV-2 viral load, or SARS-CoV-2 infectious viral titer are shown in Table 6-1. Intercurrent events are events occurring after treatment initiation that affect either the interpretation or the existence of the measurement of an endpoint. An event (eg, use of rescue medication) that occurs after an endpoint of interest (eg, hospitalization) is not considered as an intercurrent event.

Endpoint	Intercurrent event	Strategy	Description		
Proportion of COVID-19–related hospitalization or all-cause death by Day 29 Proportion of participants with all-cause hospitalization by Day 29	Discontinue randomized treatment prior to endpoint (due to AE, lack of efficacy, investigator's discretion, noncompliance with study drug, protocol violation, participant decision, lost to follow-up)	Treatment policy	Ignore the occurrence of intercurrent events (use observed outcome)		
Proportion of participants with COVID-19–related MAVs or all-cause death by Day 29 Proportion of participants with COVID-19–related MAVs by Day 29	Use of rescue medication	Treatment policy	Ignore the occurrence of intercurrent events (use observed outcome)		
Proportion of participants with all-cause death by Day 29					

Table 6-1.Handling of Intercurrent Events

Endpoint	Intercurrent event	Strategy	Description		
	Hospitalization for the treatment of COVID-19 or all-cause death	Composite policy	Hospitalization for the treatment of COVID-19 or all-cause death means never achieve symptom alleviation (censored at Day 14)		
Time to COVID-19 symptom alleviation by Day 15	Discontinue randomized treatment prior to symptom alleviation (due to AE, lack of efficacy, investigator's discretion, noncompliance with study drug, protocol violation, participant decision, lost to follow-up)	Treatment policy	Ignore the occurrence of intercurrent events (use observed outcome)		
	Use of rescue medication	Composite policy	Use of rescue medication means never achieve symptom alleviation (censor at Day 14)		
	Hospitalization for the treatment of COVID-19 or all-cause death	Treatment policy	Ignore the occurrence of intercurrent events (use observed outcome)		

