Proportion of participants with negative SARS-CoV-2 nasal swab viral load at Days 3, 5, 10, 15 Proportion of participants with negative SARS-CoV-2 nasal swab infectious viral titer at Days 3, 5, 10, 15	Discontinue randomized treatment prior to endpoint (due to AE, lack of efficacy, investigator's discretion, noncompliance with study drug, protocol violation, participant decision, lost to follow-up)	Treatment policy	Ignore the occurrence of intercurrent events (use observed outcome)		
,	Use of rescue medication	Composite policy	Use of rescue medication means never achieve negativity		

AE = adverse event; COVID-19 = coronavirus disease 2019; MAVs = medically attended visits

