- k At screening, a urine pregnancy test will be performed at the local laboratory for participants assigned female at birth and of childbearing potential. On Day 1, Day 15, and ED visits, these participants will have a serum pregnancy test performed via the central laboratory for in-person visits or a urine pregnancy test for virtual visits. At screening, a follicle-stimulating hormone test is required to confirm the postmenopausal state in participants younger than 54 years, who have stopped menstruating for at least 12 months but do not have documentation of ovarian hormonal failure, as described in Appendix 11.3 of the protocol.
- 1 A mid-turbinate nasal swab will be collected at in-person visits and used for SARS-CoV-2 RT-qPCR, potential multiplex viral PCR, potential infectious viral titer assessment, and potential resistance testing. The nasal swab must be collected by clinic/study personnel in person. For virtual visits on Days 3, 10, or 15 no samples will be collected.
- o Medically attended visit information includes any interactions with health care professionals other than study staff or designees including hospitalization; in-person emergency, urgent, or primary care visits; or any other in-person visit attended by the participant and a health care professional. The nature and cause of the visit should be identified. Medically attended visit information and oxygen supplementation information should be collected through Day 29.
- p The COVID-19 symptom questionnaire should be completed daily (at approximately the same time each day) from predose (prior to first dose on Day 1) through Day 15, and on Day 29. If a participant discontinues from the study early, the participant should complete this questionnaire during the early discontinuation visit.
- q Study drug bottle should be returned by the participant on Day 5, if the participant has already completed both doses of study drug. If the participant has study drug at the end of the Day 5 visit, the participant may return the study drug bottle on Day 10. If the Day 10 visit is virtual, drug accountability should be performed virtually and the participant will be instructed on returning the study drug bottle.

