Proportion of participants with negative SARS-CoV-2 nasal swab viral load at Days 3, 5, 10, and 15	Participants in the Virology analysis set who had SARS-CoV-2 nasal swab collected and nonmissing result of viral load reported at selected visits	Number of participants with negative SARS-CoV-2 nasal swab viral load
Proportion of participants with negative SARS-CoV-2 infectious viral titer at Days 3, 5, 10, and 15	Participants in the Virology analysis set who had SARS-CoV-2 nasal swab collected and nonmissing result of SARS-CoV-2 infectious viral titer reported at selected visits	Number of participants with negative SARS-CoV-2 infectious viral titer

4) Definition of Hospitalization

MAVs type of Emergency Room, non-ICU Hospitalization, ICU Hospitalization, and Hospitalization (unknown ward) could meet criteria for hospitalization if one of the following conditions is met:

- If the duration of the MAV is greater than 24 hours.
- If the duration is missing and end date of the MAV is 1 day after the start date.

Time to hospitalization is calculated as Start date of Hospitalization – First dose date + 1.

5) SARS-CoV-2 positive at baseline

SARS-CoV-2 positive at baseline is defined as test result from central lab.

- Cepheid's Xpert Xpress CoV-2/Flu/RSV plus (Multiplex) test result is positive for SARS-CoV-2 or
- SARS-CoV-2 RT-qPCR test result is numerical viral load result or "<2228cp/mL SARSCoV2 detected", regardless the sample was collected with less than specified volume of test solution.

GS-US-611-6273-Final Analysis-SAP-v1.0

ELECTRONIC SIGNATURES

Signed by	Meaning of Signature	Server Date (dd-MMM- yyyy hh:mm:ss)
PPD	Biostatistics eSigned	24-Jan-2024 01:01:34
PPD	Global Development Lead (GDL) eSigned	24-Jan-2024 17:55:34

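### Swab-negativity proportions: the rule for death cannot be carried out and the rescue rule clashes with the denominator, so both groups can drop out after randomization

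*SAP*

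**What the plan says.** Four parts of the SAP bear on these two endpoints.

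- **Denominator.** Appendix 3, item 3, uses "Participants in the Virology analysis set who had SARS-CoV-2 nasal swab collected and nonmissing result of viral load reported at selected visits" for viral load. For titer it asks for a "nonmissing result of SARS-CoV-2 infectious viral titer reported at selected visits".
- **Hospitalization or death.** Table 6-1 (Section 6.4) assigns COVID-19 hospitalization or all-cause death to treatment policy: "Ignore the occurrence of intercurrent events (use observed outcome". In the extracted text a page break separates this row from its endpoint names. It must belong to the swab endpoints, because symptom alleviation already has its own composite row for the same event.
- **Rescue.** The same block of Table 6-1 uses a composite: "Use of rescue medication means never achieve negativity".
- **Samples after rescue.** Section 3.7 says that viral load and titer "samples collected on or after the day when the participants are receiving additional COVID-19 treatments (see Appendix 3) will be excluded" from the analysis.

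Section 3.6.1 allows no imputation unless a method is specified, and none is visible for these endpoints. On collection, Appendix 1 footnote l states "The nasal swab must be collected by clinic/study personnel in person" and says that virtual visits on Days 3, 10 or 15 yield no sample. On titer, Protocol Section 6.3.5.1.1 says "Once viral load testing is complete, the remnant samples may be used to evaluate respiratory viral coinfection, SARS-CoV-2 infectious viral titer"; the sentence then runs into a redaction.

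**The concern.** Section 6.4 defines intercurrent events as "events occurring after treatment initiation that affect either the interpretation or the existence of the measurement of an endpoint". Death removes the measurement altogether, yet the strategy chosen for it presumes that one exists. With no imputation and a denominator of available results, a participant who has died is not counted as anything: he or she disappears from every later visit. A participant in hospital for COVID-19 who has no swab and received no listed rescue drug disappears from that visit.

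Rescue has a related fault. Table 6-1 intends a failure, but a failure must be in the denominator to be counted. If the post-rescue sample is excluded under Section 3.7, there may be no nonmissing result, and Appendix 3 gives no route by which the participant stays in.

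At stake is a comparison made among participants selected by what happened after randomization. Those removed are among the sickest, and if GS-5245 works there will be more of them on placebo.

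**Working it through.** The documents give no figure for these endpoints, so there is nothing to reproduce. The check sets the rules side by side and then sizes the effect.

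**1. Rules applied to each case**

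| Participant before the visit | Table 6-1 | Section 3.7 and Appendix 3 | Result |
|---|---|---|---|
| Died | Use observed outcome | No result, no imputation | Leaves the denominator |
| Hospitalized for COVID-19, swabbed, no rescue | Use observed outcome | Result present | Stays, as observed |
| Hospitalized for COVID-19, no swab, no rescue | Use observed outcome | No result | Leaves at that visit |
| Took a listed rescue drug | Not negative | Sample excluded; nonmissing result needed | Unsettled: failure or dropped |

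**2. Size of the death and hospitalization part**

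Let q be the share of an arm that has died or is hospitalized, unswabbed and unrescued, and p the share negative among the rest. Available results give p; counting these participants as not negative gives p(1 − q). The difference (GS-5245 minus placebo) therefore moves by p_C·q_C − p_T·q_T.

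Inputs: q_C = 2% is the planned placebo rate of the primary endpoint (SAP Section 1.3), and q_T = 0.25 × 2% = 0.5%. The values of p are assumptions. Every event is taken to precede the visit and to be unswabbed and unrescued, which is the worst case.

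- Assumed 50% v 60% negative: placebo 0.50 × 0.98 = 49.0%; GS-5245 0.60 × 0.995 = 59.7%. The difference is 10.7 points, against 10.0 under the current rule.
- Half those rates (1% v 0.25%): 49.5% v 59.85%, difference 10.35 points.
- The same p in both arms at 20%, 50% or 80%, with 2% v 0.5%: the shift is p × 1.5 points = 0.3, 0.75 or 1.2 points.
- Equal event rates: the shift is zero when p is also equal. With 50% v 60% and 2% in both arms it is 1.0 − 1.2 = −0.2 points.

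**3. Scale against the data available**

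SAP Section 2.3 says enrollment stopped with less than half of 2300 randomized, so at most about 575 per arm. That is at most 575 × 0.02 = 11.5 placebo and 575 × 0.005 = 2.9 GS-5245 participants. The standard error of a 50% v 60% difference is √[(0.25 + 0.24)/575] = 2.9 points, and more in the Virology Analysis Set, which is a subset. A shift of 0.7 points is about a quarter of that.

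**4. Titer row, conditional**

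Assume that swabs with no detectable RNA are not cultured, that 40% v 60% are RNA negative, and that half of the RNA-positive swabs are titer negative. Counting RNA-negative swabs as titer negative gives 0.40 + 0.60 × 0.5 = 70% v 0.60 + 0.40 × 0.5 = 80%. The current denominator would show 50% v 50%. If every swab is cultured, there is no loss. None of these inputs is in the documents.

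**The case against.** The strongest case on the other side is that this is a wording gap about death on minor endpoints, with very few participants affected. Much of that stands.

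- **Rescue.** A reader might infer that rescued participants count as failures while the dead vanish. The SAP does not settle this. Section 3.7 can be read as dropping rescued participants too. It could also be read as covering only the numerical analyses, but its preceding paragraph expressly preserves positive or negative results for low-volume samples, and the rescue sentence makes no such reservation.
- **Hospitalized participants.** A reader might infer that they will usually be unswabbed. The documents do not say so: Appendix 1 footnote d lets an in-person visit take place at a medical facility or elsewhere, so a swab in hospital is not barred. A swab taken there is interpretable, and treatment policy is a fair choice for it. Remdesivir is on the rescue list, so some hospitalized participants fall under the rescue rule.
- **Different strategies.** Using a composite for symptom alleviation does not oblige one here. The listed rescue drugs are antivirals and antibodies that act on the virus; hospitalization as such does not.
- **Titer.** A reader might infer that titer is compared only among RNA-positive swabs. No visible text says that RNA-undetected swabs go uncultured.
- **Redaction.** These endpoints are in no visible primary or secondary list, and text before Section 6.4 is redacted. A missing-data or sensitivity rule there cannot be excluded.
- **Other missing swabs.** Virtual visits may cost more results than death or hospitalization; the documents give no count.

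None of this answers the point about death, or the lack of a stated way to keep a rescued participant in the denominator.

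**Conclusion.** The point holds in a limited form. Treatment policy cannot be carried out after death, and the available-result denominator then removes those participants after randomization, together with anyone hospitalized for COVID-19 with neither a swab nor a listed rescue drug. Table 6-1, Section 3.7 and Appendix 3 do not agree on rescued participants and must be reconciled. The titer selection is only a possibility.

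The effect is small: about 0.7 points as an upper bound at planning rates with 50% v 60% negative, and 0.3 to 1.2 points over a common negativity of 20% to 80%. The real figure is probably lower, because the planning rates run to Day 29 while these endpoints stop at Day 15, SAP Section 2.3 reports a lower-than-expected event rate, and Section 6.5 reports very few deaths. The direction depends on the drug preventing events; in that case the current rule understates its effect. The size of the rescue part cannot be given, since the documents state no rescue rate. This is a low-priority correction that makes the rule executable and leaves the trial's main conclusions untouched.

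**What to change.** In Table 6-1 and Appendix 3 item 3:

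1. Count death as not negative at all later visits, and keep these participants in the denominator.
2. State that rescued participants stay in the denominator as not negative, despite the sample exclusion in Section 3.7.
3. Keep observed swabs for hospitalized participants. Count an unswabbed COVID-19 hospitalization as not negative only at visits that fall during the stay, at least as a sensitivity analysis, so that a real negative swab after discharge is not overridden.
4. Report the number without a result at each visit by arm and reason, with virtual visits as a separate reason.
5. State whether swabs without detectable RNA are cultured. If they are not, count them as titer negative.

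The cost is a few lines of SAP and programming text plus one table, with no new data. Under SAP Section 1, changes made after finalization are documented in the clinical study report. Item 5 adds an assumption that should be stated: no detectable RNA means no infectious virus. If all swabs are cultured, item 5 changes nothing.

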3. GENERAL CONSIDERATIONS FOR DATA ANALYSES

Analysis results will be presented using descriptive statistics. For categorical variables, the number and percentage of participants in each category will be presented; for continuous variables, the number of participants (n), mean, standard deviation (SD) or standard error (SE), median, first quartile (Q1), third quartile (Q3), minimum, and maximum will be presented.

By-participant listings will be presented for all participants in the All Randomized Analysis Set and sorted by participant identification (ID) number, visit date, and time (if applicable). Data collected on log forms, such as adverse events (AEs), will be presented in chronological order within the participant. The treatment group to which participants were randomized will be used in the listings. Age, sex at birth, race, and ethnicity will be included in the listings, as space permits.

SARS-CoV-2 viral load will be used throughout the SAP for SARS-CoV-2 RT-qPCR viral load.

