3.1.4. Virology Analysis Set

The Virology Analysis Set includes all randomized participants who received at least 1 dose of study drug and had baseline SARS-CoV-2 viral load \geq lower limit of quantification (LLOQ). Refer to Section 3.7 for the definition of LLOQ.

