- For baseline questionnaire data, the last nonmissing value on or prior to the first dosing date of study drug will be selected. If there are multiple records on or prior to the first dose date, the record prior to and closest to the first dose date and time will be used if available; otherwise the record after and closest to the first dose date and time will be used.
- For baseline data other than questionnaire, the last nonmissing value on or prior to the first dosing date of study drug will be selected, unless specified differently. If there are multiple records on the same day, the baseline value will be selected as follows:
 - For continuous data:
 - For SARS-CoV-2 viral load and SARS-CoV-2 infectious viral titer, if there is more than 1 record on the selected day, the latest value will be selected. If there are multiple records with the same time or no time recorded on the same day, the geometric mean value (copies/mL) will be taken.
 - For other continuous data, the average of the measurements will be taken.
 - For categorical data:
 - For SARS-CoV-2 positivity based on RT-qPCR, positivity based on infectious viral titer and Multiplex viral PCR, the worst severity (ie, a positive result, if available) will be selected.
 - For other categorical data, the lowest severity will be selected.

- For postbaseline values:
 - The record closest to the nominal day for that visit will be selected.
 - If there are 2 records that are equidistant from the nominal day, the later record will be selected.
 - If there is more than 1 record on the selected day, values will be selected for analysis as follows:
 - For SARS-CoV-2 viral load and SARS-CoV-2 infectious viral titer, if there is more than 1 record on the selected day, the latest value will be selected. If there are multiple records with the same time or no time recorded on the same day, the geometric mean value (copies/mL) will be taken.
 - For time to symptom alleviation, all records within the analysis visit window will be used.
 - For questionnaire data to be summarized, if there is more than 1 record on the selected day, the latest value will be selected.
 - For other parameters, if there is more than 1 record on the selected day, the average will be taken for continuous data and the worst severity will be taken for categorical data, unless otherwise specified.

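### The proportion with negative infectious titer is computed in a set defined by baseline RNA, so participants already titer negative on Day 1 dilute the treatment contrast

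*SAP*

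**What the plan says.** SAP Appendix 3, item 3 gives the denominator for this endpoint as "Participants in the Virology analysis set who had SARS-CoV-2 nasal swab collected and nonmissing result of SARS-CoV-2 infectious viral titer reported at selected visits" and the numerator as "Number of participants with negative SARS-CoV-2 infectious viral titer". Neither refers to the baseline titer.

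Entry to the set is defined in SAP Section 3.1.4: "The Virology Analysis Set includes all randomized participants who received at least 1 dose of study drug and had baseline SARS-CoV-2 viral load" at or above the LLOQ. Section 3 fixes the meaning of the term: "SARS-CoV-2 viral load will be used throughout the SAP for SARS-CoV-2 RT-qPCR viral load". The entry condition is therefore an RNA measurement. Section 3.7 gives its limit: "A value of 1114 copies/mL (half of the LOQ 2228 copies/mL) will be used to calculate descriptive statistics".

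Infectious titer is a different assay, with a limit of 200 PFU/mL and its own qualitative result. For a value below that limit with a negative qualitative result, Section 3.7 states: "A value of 50 PFU/mL (1/4 of the LOQ 200 PFU/mL) will be used to calculate descriptive statistics". The plan thus recognises titer-negative samples as a category separate from the RNA result.

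Section 3.8.3 has a rule for choosing the baseline record when several exist on one day: "For SARS-CoV-2 positivity based on RT-qPCR, positivity based on infectious viral titer and Multiplex viral PCR, the worst severity" is taken. Baseline titer positivity is therefore already a specified variable.

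**The concern.** A participant can have quantifiable RNA on Day 1 and no infectious virus recovered. Under the planned definition that participant is counted as negative on Day 3, 5, 10 or 15 whenever the titer is negative then, although there was no positive titer to clear. The reported proportion mixes participants who cleared infectious virus with participants who had none detected at the start, and the summary does not separate them.

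The two nearest endpoints avoid this. RNA negativity uses the same set, so every participant starts with quantifiable RNA. For symptom alleviation, Appendix 3, item 1 removes participants who reported none of the symptoms at baseline. Only the titer endpoint lacks a matching starting condition.

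At stake is how a supportive antiviral result can be read. Both arms' proportions move toward 100%, the difference shrinks, and a chance imbalance in baseline titer status appears directly in the observed difference.

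**Working it through.** **No stated figure to reproduce.** The documents give no expected proportion, effect or power for this endpoint. The imputation values around it are consistent: 2228/2 = 1114 copies/mL and 200/4 = 50 PFU/mL.

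**Inputs.**
- From the SAP: set membership by baseline RNA (3.1.4); numerator and denominator (Appendix 3, item 3); separate titer assay (3.7).
- Assumed, because the documents are silent: q, the share of the set that is titer negative at baseline, from 0.10 to 0.70; negativity at a visit among baseline positives of 50% on placebo (pP) and 70% on active (pT); 300 participants per arm for the power illustration.

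**Formula.** If baseline negatives stay negative in both arms, each arm's proportion is q + (1 − q)p. The risk difference is then (1 − q)(pT − pP).

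| q | Placebo | Active | Difference (points) |
|---|---|---|---|
| restricted to baseline positives | 50% | 70% | 20 |
| 0.10 | 55% | 73% | 18 |
| 0.40 | 70% | 82% | 12 |
| 0.60 | 80% | 88% | 8 |
| 0.70 | 85% | 91% | 6 |

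On the same assumptions, the share of placebo negatives who were already negative on Day 1 is q/[q + (1 − q)pP]. That is 0.10/0.55 = 18% at q = 0.10 and 0.40/0.70 = 57% at q = 0.40.

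**If baseline negatives do not all stay negative.** Let them be negative at the visit with probability r in both arms. The term q·r then cancels from the difference. At q = 0.40 and r = 0.90, placebo is 0.36 + 0.30 = 66%, active is 0.36 + 0.42 = 78%, and the difference is still 12 points. The factor (1 − q) needs only equal r in the two arms.

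**Effect of restricting, despite the smaller N.** Power is from a two-sided 0.05 two-proportion normal approximation with pooled null variance.
- q = 0.40, as written: 300 per arm, 70% versus 82%. The null SE is √(2 × 0.76 × 0.24/300) = 0.0349 and the alternative SE is √((0.21 + 0.1476)/300) = 0.0345. Then (0.12 − 1.96 × 0.0349)/0.0345 ≈ 1.50, giving power 0.933.
- q = 0.40, restricted: 180 per arm, 50% versus 70%. Power is 0.975.
- q = 0.60: 0.763 as written, 0.890 restricted.
- q = 0.10: 0.996 as written, 0.998 restricted.

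With 70% versus 85% among baseline positives and q = 0.40, power is 0.899 as written and 0.929 restricted.

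**Chance imbalance.** With no treatment effect and common negativity p among baseline positives, a difference d between arms in q shifts the observed difference by d(1 − p). For d = 5 points and p = 0.50 the shift is 2.5 points.

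**The case against.** The strongest reply is that the SAP defines a status at each visit, not a conversion. As a status in a randomized, RNA-positive set, the comparison is valid: baseline titer is a pre-treatment feature, balanced in expectation. This stands. A reader might infer bias between arms or an inflated type I error, and the documents support neither. Table 6-1 does treat rescue use as never attaining negativity, which leans toward a clearance reading, but that is a rule for one intercurrent event and not the endpoint definition.

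A reader might also infer that part of the result is fixed before dosing and that baseline negatives tell us nothing. That is too strong. Protocol Section 4.2 enrols within 5 days of symptom onset, so a later positive titer is possible, and rescue use turns a negative into a non-negative. If treatment affected later positivity, these participants would contribute to the contrast. What they cannot show is conversion from positive to negative.

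The weight is limited. Titer negativity is not among the alpha-controlled or other secondary efficacy endpoints in SAP Section 6.2, and the Day 5 RNA change is untouched. Enrollment stopped early for a low primary event rate (SAP Section 2.3), but the documents do not show that titer negativity thereby gains a larger role.

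Text between SAP Sections 6.2.1 and 6.4 is redacted, so a baseline-positive analysis may be described there. The visible Appendix 3 row carries no such condition. SAP Section 3.3 allows covariate-adjusted sensitivity analyses for baseline imbalance, and Section 3.4 allows subgroups by baseline RNA level. Both are optional and neither names titer.

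Finally, titer testing is described as potential (Protocol Table 1, footnote l) and uses remnant sample (Section 6.3.5.1.1). Some participants may lack a baseline titer, and a simple restriction would drop them silently. This stands and shapes the fix.

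**Conclusion.** The concern holds as one of dilution and interpretability in a supportive virology summary. On the visible text, participants already titer negative at baseline are kept in the denominator and counted as negative, unlike in the parallel RNA and symptom endpoints.

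The size depends on q, which is unknown. At q = 0.10 the loss is 2 points out of an assumed 20, at q = 0.40 it is 8, and at q = 0.70 it is 14. These figures rest on the assumed response rates and on baseline negatives remaining negative equally often in both arms. In the cases computed, restricting to baseline positives gave slightly to clearly higher power despite fewer participants. Nothing here affects the primary, key secondary or RNA viral load analyses.

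**What to change.** In SAP Appendix 3, item 3, define the denominator of the main titer summary as Virology Analysis Set members who have a positive baseline infectious titer and a titer result at the visit. Report by arm how many had a negative and how many had a missing baseline titer. Keep the current denominator as a supportive summary, so that participants with unknown baseline titer remain visible.

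Restricting on a pre-treatment value keeps the randomized comparison valid. The change is one line of wording and a filter on a variable for which Section 3.8.3 already gives a baseline rule. The cost is a smaller main denominator, which loses participants with missing baseline titer as well as those who were negative. If the SAP is already final, its Section 1 provides the route: document the change in the clinical study report.
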